5.2 Secondary Objectives

The secondary objectives are the following:

1. To evaluate safety through the monitoring of device-related and procedure-related adverse events (AEs) and all serious adverse events (SAEs), from start of ablation through 1-year post-ablation.
2. To establish device and procedure effectiveness by following patients for 1-year post-ablation to ensure completeness and durability of treatment effect, based on standard endpoints in microwave ablation, as follows:
 - a. Primary efficacy rate
 - b. Secondary efficacy rate
 - c. Local soft lesion recurrence
 - d. Length of hospital stay (LOS)
 - e. Hospital readmission rate.
3. To calculate length of hospital stay (LOS), measured from post-ablation to discharge.
4. To calculate hospital readmission rate, defined as any readmission to the hospital within 30 days of the first ablation procedure (Visit 2A).

5.3 Exploratory Objectives

The exploratory objectives are the following:

1. To assess the quality of life post microwave ablation of the lung throughout the 1 year \pm 1 month follow-up period.
2. To assess the level of pain during the initial 30 days \pm 7 days post-ablation.

6.0 ENDPOINTS

6.1 Primary Endpoints

The primary endpoints include the following:

- Device user experience: The data will come from the User Experience Survey, which will be completed by the treating physician following each ablation procedure.
- Technical success, defined as: ablation of the target lesion according to the protocol and covered completely, with an adequate margin, as defined by the performing physician (that is, the ablation zone completely overlaps or encompasses the target lesion plus an ablative margin), as assessed by cone beam CT imaging, immediately following the procedure.
- Technique efficacy, defined as ablation of the target lesion according to the protocol and covered completely, with an adequate margin, as defined by the performing physician (that is, the ablation zone completely overlaps or encompasses the target lesion plus and ablative margin). Technique efficacy will be assessed using CT imaging at Visit 3, which is 30 days \pm 7 days after the first ablation procedure.

6.2 Secondary Endpoints

The secondary endpoints include the following:

- Any complications attributable to the procedure, including all device-related, procedure-related, and serious adverse events (SAEs), evaluated from the start of ablation through 30 days \pm 7 days post application of ablation and from the start of ablation through end of follow-up (1-year post-ablation) or early discontinuation.
- Primary efficacy rate, defined as the percentage of target soft tissue lesions successfully eradicated following the ablation procedure, as assessed using CT imaging.
- Secondary efficacy rate, defined as the percentage of soft tissue lesions that have undergone successful repeat ablation following identification of local soft tissue lesion progression, as assessed using CT imaging.
- Target lesion recurrence, defined as reappearance of the lesion at the treated site, as assessed using CT imaging.
- Length of stay, measured from after the ablation procedure until the patient is discharged home.
- Hospital readmission rate, defined as any readmission to the hospital within 30 days.

6.3 Additional Measurements / Data Collected

- Patient demographics and baseline characteristics.
- Quality of life (QOL) and pain.
- Relevant medical and surgical history.
- [REDACTED] Soft tissue lesion details (size, lesion type, location, shape). [REDACTED]
[REDACTED]
[REDACTED]

[REDACTED]

7.0 INVESTIGATIONAL PLAN

7.1 Overall Study Design and Plan – Description

This is a multicenter, single-arm study for NEUWAVE Flex Microwave Ablation System in the ablation of soft tissue lesions of the lung for medically inoperable patients or those who elect not to have surgery. An experienced interventional pulmonologist or thoracic surgeon will determine whether a patient is “medically inoperable.” Indicators defining medically inoperable are, as follows: post-op predictive FEV1 < 40%; DLCO < 40%; hypoxemia or hypercapnia diabetes with end-organ damage; or, severe cerebral, cardiovascular, peripheral vascular disease, or chronic heart disease.

Prospective patients will be informed about the nature of the research, given the ICF to read, and if the patient understands the content, will be asked to provide consent by signing the ICF. Individuals scheduled for microwave ablation of the lung will be enrolled after providing informed consent and meeting study entry criteria. Patients will be followed for approximately 1 year following the first ablation procedure for safety and efficacy outcomes.

[REDACTED] Only participants who withdraw or are terminated prior to the planned intrabronchial flexible probe ablation procedure will be replaced.

[REDACTED]

[REDACTED]

[REDACTED]

The study will end when all patients have completed the 12-month, post-ablation follow-up period or have withdrawn early.

7.2 Enrollment

A target total of approximately 40 patients, [REDACTED] will be enrolled across multiple study sites in the United States. A subject who signs the consent is considered screened and once treated they are considered enrolled into the study.

7.3 Inclusion Criteria

Patients satisfying the following criteria will be eligible to participate in this study:

1. Signed informed consent.
2. Patients \geq 18 years old.
3. Performance status 0-2 (Eastern Cooperative Oncology Group classification [ECOG]).

4. Willing to fulfill all follow-up requirements.
5. Medically inoperable primary soft tissue lesion of the lung or patient election not to have surgery.

(Medically inoperable is defined per the following indicators: post-op predictive FEV1 < 40%; DLCO < 40%; hypoxemia or hypercapnia diabetes with end-organ damage; or severe cerebral, cardiovascular, peripheral vascular disease, or chronic heart disease.)

6. A soft tissue lesion ≤ 2 cm in the outer two-thirds of the lung and not closer than 1 cm to the pleura. Lesion size must be measured with at least 2-dimensional (2D) imaging. Only one lesion meeting the inclusion criteria may be treated during the day of ablation (Visit 2A). However, additional primary disease lesions may be present on the day of ablation.

(Outer two-thirds of the lung is defined as peripheral beyond the segmental airway, past the segmental bronchi, such that proximal endobronchial soft tissue lesions are avoided; soft tissue lesions should not be contiguous with the pleura.)

7.4 Exclusion Criteria

Patients who meet any of the following criteria will not be eligible to participate in this study:

1. Scheduled concurrent procedure for the target soft tissue lesion other than those indicated by the study protocol.
2. Pregnant or breastfeeding.
3. Physical or psychological condition that would impair study participation.
4. Patients with uncorrectable coagulopathy at time of screening.
5. Patient with implantable devices, including pacemakers or other electronic implants.
6. Prior pneumonectomy or bronchiectasis.
7. Severe neuromuscular disease.
8. Platelet count $\leq 50,000/\text{mm}^3$.
9. ASA (American Society of Anesthesiologists) score of ≥ 4 .
10. Inability to tolerate anesthesia.
11. Expected survival less than 6 months.
12. Clinically significant hypertension.
13. Chronic, continuous ventilator support, which uses bi-level positive airway pressure (PAP) to improve lung function for severe conditions. (However, intermittent PAP for non-pulmonary conditions, such as sleep apnea, is permitted.)
14. Endobronchial soft tissue lesions proximal to the segmental airways.
15. Convex probe EBUS (CP-EBUS) lymph node sampling that results in a positive diagnosis of malignancy.
16. Imaging findings of active pulmonary infection.

17. The patient was judged unsuitable for study participation by the Investigator for any other reason.

7.5 Prior and Concomitant Therapy

Patients may continue with their current medical care throughout the duration of the study, including medications. All concomitant medications will be recorded on the relevant eCRF page. Do not record components of the anesthesia medications used for the ablation procedure.

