
Exclusion criteria
	
 1. Scheduled concurrent procedure for the target soft tissue lesion other than those that are lung related. 2. Pregnant or breastfeeding. 3. Physical or psychological condition that would impair study participation. 4. Patients with uncorrectable coagulopathy at time of screening. 5. Patient with implantable devices, including pacemakers or other electronic implants. 6. Prior pneumonectomy or bronchiectasis. 7. Severe neuromuscular disease. 8. Platelet count \leq 50,000/mm³. 9. ASA (American Society of Anesthesiologists) score of \geq 4. 10. Inability to tolerate anesthesia. 11. Expected survival less than 6 months. 12. Clinically significant hypertension. 13. Chronic, continuous ventilator support, which uses bi-level positive airway pressure (PAP) to improve lung function for severe conditions. (However, intermittent PAP, for non-pulmonary conditions, such as sleep apnea, is permitted.) 14. Endobronchial soft tissue lesions proximal to the segmental airways. 15. CP-EBUS lymph node sampling that results in a positive diagnosis of malignancy. 16. Imaging findings of active pulmonary infection. 17. The patient was judged unsuitable for study participation by the Investigator for any other reason.

Test product
	
  
 NEUWAVE Flex Microwave Ablation System	
 
 Product Code	Description	
   
 NWF1US1N	NEUWAVE Flex Microwave Ablation System, 120 Vac DR-000770	
 
 [REDACTED]	[REDACTED]	
 
 [REDACTED]	[REDACTED]	
 
 [REDACTED]	[REDACTED]	
 
 [REDACTED]	[REDACTED]	
  
	NEUWAVE Flex Microwave Ablation System		Product Code	Description	NWF1US1N	NEUWAVE Flex Microwave Ablation System, 120 Vac DR-000770	[REDACTED]	[REDACTED]	[REDACTED]	[REDACTED]	[REDACTED]	[REDACTED]	[REDACTED]	[REDACTED]
NEUWAVE Flex Microwave Ablation System															
Product Code	Description														

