8.2.1 Visit 1 – Screening

The screening assessments for this visit may occur over several dates within 30 days prior to Visit 2.

Patients will be selected for microwave ablation based on the pre-procedure investigations and the Investigator's interpretation of the clinical picture. Eligible patients will be provided with the study information, including the ICF.

The following screening assessments will occur prior to the study procedure:

- Patients must be given ample time to review and sign the ICF.
- Collect demographic information (age at time of Visit 1, sex, race, ethnicity).
- Review and collect medical and surgical history, including date of diagnosis of soft tissue lesion under study, radiation history, and smoking status.
- Collect height and body weight for BMI
- Evaluate ECOG performance status.
- Record the American Society of Anesthesiologists (ASA) score, which is a global score that assesses the physical status of patients before surgery.
- Record all prior medications taken within 30 days of Visit 2 and all current medications, including but not limited to chemotherapy, steroids, anti-inflammatories, NSAIDs, hormonal therapy, homeopathic/natural medications, nutritional supplements, and antibiotics.
- Review inclusion/exclusion criteria and determine if the patient is eligible to participate in the study.
- QOL questionnaires European Organization for Research and Treatment of Cancer (EORTC) QLQ-C30 and the lung-specific QLQ-LC13. The questionnaires may be administered over the phone, as needed.
- Numeric Pain Rating Scale.
- CT scan of the lung to determine soft tissue lesion details (e.g., size, lesion type, location, shape).
- [REDACTED] send the scan to the central radiologist for independent review (refer to the Central Radiology Review manual).
- Obtain PFTs, which may include spirometry, diffusion capacity (also called the DLCO [diffusing capacity of the lung for carbon monoxide]), lung volume tests, pulse oximetry, and FeNO tests.
- Laboratory tests. If the following tests (based on the study site's SOC) will be completed within 30 days of Visit 2, then they do not need to be repeated at the

Screening visit:

- CBC (with differentials).
- Coagulation tests (APTT, INR, PT, PTA, PTT).
- Serum pregnancy test, for women of childbearing potential only.
- Any genetic markers relevant to the lesion, if done per SOC.

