8.2.2 Visit 2 – Ablation Procedure Through Discharge (Visit 2B)

[REDACTED]

[REDACTED]

On the day of ablation, cone beam CT scans will be done at the timepoints listed in the section below.

Visit 2A: Intraoperative (Ablation)

Data collected before and during the procedure:

- Administer antibiotics prior to the ablation procedure.
[REDACTED]
- Measure and record the size of the lesion to confirm inclusion criteria (lesion must be ≤ 2 cm).
- Prior to ablation, confirm that the patient still meets inclusion and exclusion criteria (tests not needed to be repeated).
- Collect height and body weight for BMI, and evaluate ECOG performance status (prior to ablation).
- Record all concomitant medications, including but not limited to chemotherapy, steroids, anti-inflammatories, NSAIDs, hormonal therapy, homeopathic /natural medications, nutritional supplements, and antibiotics. Do not record components of the anesthesia medications used for the ablation procedure.
- Record all concomitant procedures.
- QOL questionnaires EORTC QLQ-C30 and the lung-specific QLQ-LC13 (prior to ablation). The questionnaires may be administered over the phone, as needed.
- Numeric Pain Rating Scale (prior to ablation).

[REDACTED]

[REDACTED]

[REDACTED]

[REDACTED]

[REDACTED]

[REDACTED]

[REDACTED]

[REDACTED]

[REDACTED]

[REDACTED]

[REDACTED]

[REDACTED]

[REDACTED]

[REDACTED]

[REDACTED]

[REDACTED]

- User Experience Survey answered by the treating physician post-ablation (available as a separate document).
- Evaluate technical success, defined as ablation of the target lesion according to the protocol and covered completely, with an adequate margin, as defined by the performing physician (that is, the ablation zone completely overlaps or encompasses the target lesion plus an ablative margin).

[REDACTED]

- Radiation exposure from the CT scans.
- Record any AEs/SAEs that occur from the start of the ablation.

Visit 2B: Discharge

After the ablation procedure, the patient will be observed for up to 23 hours and afterwards discharged from the study site (except in cases where the Investigator deems it is necessary for the patient to remain hospitalized). During that 23-hour period, the following assessments will occur:

- Record all concomitant medications.
- Record all concomitant procedures.
- QOL questionnaires EORTC QLQ-C30 and the lung-specific QLQ-LC13. The questionnaires may be administered over the phone, as needed.
- Numeric Pain Rating Scale.

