9.5 Secondary Endpoint Analyses

The study protocol indicates that summaries will be provided for the primary and secondary efficacy rates as well as hospital readmission rates. However, data relevant to these endpoints will only be listed given the reduction in overall sample size. The number and percentage of subjects experiencing target lesion recurrence at any time during following will be summarized and an exact 95% confidence interval will be estimated, but the Kaplan-Meier analysis described in the study protocol will not be performed.

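### The planned recurrence rate counts a target lesion as recurrence-free even if it received other local treatment after ablation

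*Protocol*

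**What the plan says.** **Purpose.** Protocol 5.2, secondary objective 2, follows patients for a year "to ensure completeness and durability of treatment effect". Section 6.2 defines recurrence as the lesion reappearing on CT at the treated site. The definition has no condition on other treatment.

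**Analysis.** SAP 9.5 states: "The number and percentage of subjects experiencing target lesion recurrence at any time during following will be summarized", with an exact 95% interval. It drops the Kaplan-Meier estimate of protocol 10.9 and moves the primary and secondary efficacy rates to listings. SAP 9.10 plans no sensitivity analysis. Table 8 (site assessment) and Table 22 (independent reviewer) each have one Yes row for recurrence.

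**Other treatment.** Section 7.5 leaves current care open: "Patients may continue with their current medical care throughout the duration of the study, including medications". Screening collects history, "including date of diagnosis of soft tissue lesion under study, radiation history, and smoking status", and Visit 2A says "Record all concomitant medications, including but not limited to chemotherapy, steroids". In the SAP these data appear only in Listings 9 (radiation history), 27 (concomitant procedures) and 28 (concomitant medications).

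**Eligibility.** Exclusion 1 exists in two versions. Section 7.4 has "Scheduled concurrent procedure for the target soft tissue lesion other than those indicated by the study protocol". The synopsis has "Scheduled concurrent procedure for the target soft tissue lesion other than those that are lung related".

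**The concern.** Recurrence is the one result beyond Day 30 that the SAP still summarises as a rate for durability. The study has a single arm, so no comparison separates the effect of ablation from that of a later treatment at the same site. If a target lesion is given another local treatment before it has reappeared, a clean CT at Month 12 reflects both treatments. The planned table credits it to ablation.

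At stake is how the 1-year result reads: ablation alone held the lesion, or the lesion was controlled by whatever was done to it. No hypothesis test, primary endpoint or sample size depends on this.

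**Working it through.** **1. What the planned row does with each pattern.**

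- Lesion reappears on CT and is then treated again: counted as a recurrence, because SAP 9.5 counts recurrence at any time. No problem.
- Coverage incomplete at Day 30, lesion then irradiated, no later reappearance: a failure on technique efficacy, but recurrence-free in the next row of the same table.
- Coverage complete at Day 30, other local treatment given before any reappearance: a success on both rows.
- Radiation to the lesion before ablation, no reappearance: recurrence-free, but with no clear direction of bias (see the objection).

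The gap is the second and third patterns.

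**2. Does exclusion 1 close it?** The section 7.4 version bars a non-protocol procedure on the target lesion that is scheduled at entry. The synopsis version exempts lung-related procedures. Neither version reaches treatment decided on after enrolment.

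**3. Size.** The plan states no recurrence figure and no rate of other treatment, so there is nothing to reproduce. Inputs:

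- n = 10 subjects ablated (SAP 7), all assumed to be in the denominator.
- r = observed recurrences (assumed).
- k = subjects recorded as recurrence-free who had non-study local treatment of the target lesion after ablation (assumed, 0 to 3).

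Planned rate = r/n. Combined rate = (r + k)/n. Each subject contributes 1/10 = 10 points.

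The exact (Clopper-Pearson) 95% limits for x/n are the 2.5% quantile of Beta(x, n − x + 1) and the 97.5% quantile of Beta(x + 1, n − x). For x = 0 the lower limit is 0 and the upper limit is 1 − 0.025^(1/n). With n = 10 that upper limit is 30.8%.

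With r = 0:

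| k | Planned row | Combined row | Such subjects left out |
|---|---|---|---|
| 0 | 0/10 = 0% (0 to 30.8) | 0/10 = 0% (0 to 30.8) | 0/10 = 0% (0 to 30.8) |
| 1 | 0/10 = 0% (0 to 30.8) | 1/10 = 10% (0.3 to 44.5) | 0/9 = 0% (0 to 33.6) |
| 2 | 0/10 = 0% (0 to 30.8) | 2/10 = 20% (2.5 to 55.6) | 0/8 = 0% (0 to 36.9) |
| 3 | 0/10 = 0% (0 to 30.8) | 3/10 = 30% (6.7 to 65.2) | 0/7 = 0% (0 to 41.0) |

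With r = 2 and k = 2, the planned row gives 2/10 = 20% (2.5 to 55.6), the combined row 4/10 = 40% (12.2 to 73.8), and leaving the two out 2/8 = 25% (3.2 to 65.1).

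The planned row does not change with k, so a reader of Table 8 or 22 cannot tell these cases apart. The combined rate is never below the planned rate, since k cannot be negative.

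**The case against.** Several points on the other side stand.

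- **Eligibility is not the fault.** A reader might infer that the trial should have excluded or washed out earlier anticancer treatment. The documents do not support that as the point. The section 7.4 version of exclusion 1 does bar scheduled non-protocol procedures on the target lesion. Leaving care to the treating physician is a stated design choice (section 4.0). Enrolment has closed, so no eligibility change is possible.
- **Resection is the weakest example.** Inclusion 5 admits patients who are medically inoperable or who elect not to have surgery. The second group could later change their minds, so the case is not empty.
- **Earlier treatment need not flatter the device.** A reader might infer that all other therapy lowers the recurrence rate. That is not shown for treatment before ablation. Lesion size is measured again at Visit 2A, and a lesion that persisted after radiation could be harder to control.
- **Some text is not visible.** Footnotes to the schedule of assessments and parts of the follow-up sections are redacted. Absence of a limit can be asserted only for the visible text.
- **The data will be listed.** With 10 subjects, a reader could link Listings 9, 27 and 28 to recurrence line by line.
- **The intervals overlap heavily**, and the counts used above are assumptions.

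What does not stand is that the listings are enough. The percentage and its interval are what will be quoted for durability, and no row or footnote warns that other local treatment is folded into them.

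**Conclusion.** The concern holds for non-study local treatment of the target lesion given after ablation and before any recurrence. As written, SAP 9.5 and Tables 8 and 22 count such a subject as recurrence-free, and exclusion 1 does not prevent the situation from arising after enrolment. Each case is worth 10 points if all 10 ablated subjects are in the denominator. With no observed recurrences, 0% (0 to 30.8) would read 10% (0.3 to 44.5) with one case and 20% (2.5 to 55.6) with two.

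The actual number of cases is not in the documents and may be zero, so a reader should not infer that the rate is known to be biased. The finding is that the planned table cannot show whether it is. This affects the interpretation of a secondary descriptive endpoint. It is worth correcting because that endpoint carries the durability claim.

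**What to change.** In SAP 9.5 and in Tables 8 and 22, keep the planned recurrence row and add:

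1. The number of subjects with non-study local treatment of the target lesion (radiation, resection or another ablation modality) after ablation and before any recurrence.
2. A combined row, recurrence or non-study local treatment of the target lesion, as x/n with an exact 95% interval. Each subject counts once. Show it beside the recurrence rate, not in its place, wherever durability is claimed for secondary objective 2.
3. A descriptive footnote giving the number who had radiation to the target lesion before ablation and the number on systemic anticancer therapy at or after ablation. State no direction of bias for earlier therapy.

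Separately, reconcile the synopsis and section 7.4 versions of exclusion 1 and state which one governed enrolment.

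**Cost.** Two rows in each of two tables, one footnote and some programming, mostly from data already collected. The visible text does not show that the procedure and radiation forms identify the target lesion, so linking them needs case-level review of 10 subjects. The durability figure may look less favourable. If the count is zero, the new rows say so and strengthen the claim. Patient care does not change. If the SAP is already final, SAP 9.1 allows the addition to be identified in the output and documented in the clinical study report.
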